4.4. Discontinuation and withdrawal of subjects

4.4.1. Withdrawal of subjects

Subjects are free to discontinue their participation in the study at any time without prejudice to further treatment. In either case, serious adverse events where relation to IMP cannot be excluded, will be followed up. Other reasons for discontinuing a subject are incorrect enrolment and subjects lost to follow-up.

Any subject fulfilling any of the pre-defined exclusion criteria will be withdrawn from the study:

- participating patients withdrawing their consent, subjects are free to discontinue their participation in the study at any time without prejudice to further treatment
- participating patients developing allergic reactions or any other SAE possibly due to methenamine hippurate
- participating patients requiring long term use of alkalinizing substances (such as antacids) during the first six months when taking IMP as alkalinizing substances reduces the effect of methenamine hippurate and should be avoided
- participating patients developing serious illness making it impossible for them to continue taking the study tablets.

Simultaneous intake of sulphonamide antibiotics can increase risk of crystalluria. Therefore, methenamine hippurate will temporarily be paused if the participant is prescribed a course of sulphonamide antibiotics, but will continue with IMP after that.

Participating patients developing clinically significant dehydration will not receive IMP until clinically resolved dehydration, but will continue with IMP after that.

Those patients who have to prematurely stop taking the IMP, except for patients' withdrawing their consent, will be followed up in the same framework of the study and in the same way as participants receiving IMP.

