8. STATISTICS

8.1. Sample size calculation

The sample size calculation is made for the primary objective described in section “2 Study Objectives and Endpoints”.

- We assume these selected older individuals will have an average of two courses of antibiotics for suspected UTI every six months (4).
- We assume a 25% reduction of antibiotic prescriptions during the first six-month period after introduction of methenamine hippurate. Hence the intervention group would have an average of 1.5 while the control group is assumed to remain around 2.0. We assume the standard deviation in each group to be 1.5. This will result in an effect size of 0.33 (small effect). We decided a smaller effect size would not be worth looking for.
- We assume the level of significance being 0.05, the power to be 0.80 and that a two tailed test is explored.
- We use Student's t-test as the statistical analysis but also calculate for Mann-Whitneys test (to be used if the outcome variable is not normally distributed). The planned statistical method to be used will be multivariate linear regression. Student's t-test and Mann-Whitneys test are used as surrogate methods to estimate sample size.

Under the assumptions given above an effective sample size of 286 patients (143+143) is required if t-test can be used. However, if Mann-Whitney's test is required we need 298 (149+149) patients. To achieve an effective sample size of at least 298 after considering a 25% loss to follow-up we aim to include at least 397 patients. We will aim to include 400 patients.

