5. STATISTICS

5.1. Statistical analysis

It is the intention to adjust all analysis for the following confounding variables obtained at visit 1

- patient's age
- urine acidity (pH)
- number of antibiotic courses for UTIs in the 12 months preceding inclusion in the study
- presence of urease/stone-producing bacteria in urine culture day 1 such as *proteus*, some *klebsiella* species, *Morganella morganii*, *Corynebacterium urealyticum* and *providencia*
- use of local oestrogen
- patient has diabetes mellitus
- obesity defines as BMI ≥ 30
- presence of known mild abnormality of the urogenital tract
- if the patient is sexually active.
- If the patient previously have experienced urinary tract stone

Phylogenetic subtype of pure cultures of *E.coli* in the urine culture at inclusion will be analysed in a separate analysis if the number of cultures available for typing are not too small.

The statistical calculation relates to the study objectives described in section “2 Study Objectives and Endpoints”:

- 1 Negative binomial multivariable regression will be used where number of UTI antibiotic treatments will be the dependent variable. Group allocation together with the confounding variables above will be independent variables. Histograms of the dependent variable will determine if we need to adjust for zero inflation (or any other inflation).
- 2a Will be analysed using the same statistical approach as objective 1 above.
- 2b Will be analysed using the same statistical approach as objective 1 above. Number of UTIs will be the dependent variable.
- 2c The outcome variable is measured at first day of a UTI using a six grade ordinal scale. The median value from all UTIs will be used if the patient has more than one episode of UTI. Data will be analysed using ordinal multivariable logistic regression.
- 2d Will be analysed using the same statistical approach as objective 1 above. Number of days with symptoms will be the dependent variable. The median value from all UTIs will be used if the patient has more than one episode of UTI.
- 2e Will be analysed using the same statistical approach as objective 1 above. Number of severe events such as pyelonephritis or hospital admission will be the dependent variable.

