5.1.1. Intention to treat analysis and missing data

The primary statistical analysis is intention to treat including all patients randomized contributing with a full set of baseline observations. A sensitivity analysis will be done also including patients randomized with incomplete baseline observations where we may have to omit one or a few baseline covariates from the regression analyses.

Patients leaving the study completing at least three but less than six of the first six months will contribute with data up until they leave the study and this data will be extrapolated as if it was six months.. If they remained for less than three months their observations will be imputed with the mean from similar patients. Similar patients are defined as having an age of \pm five years and belonging to the same intervention group. Patients leaving during the second six months period will also contribute with data as described above.

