5.1.3. Per protocol analysis

A per protocol analysis including patients consuming at least 80% of dispensed study medication will be made.

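### SAP 5.1.1's leaver rules also reach objective 2e, so in that analysis an observed pyelonephritis or UTI admission can be replaced by a near-zero mean or counted up to twice

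*SAP*

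**What the plan says.** **Leaver rules (SAP 5.1.1).** The rules are written for patients leaving the study, with no outcome named. Women who complete at least three but less than six of the first six months contribute their own data, scaled to six months. For shorter stays, "If they remained for less than three months their observations will be imputed with the mean from similar patients". Similar means same arm and age within five years. Leavers in the second six months are handled in the same way. SAP section 6 gives the reason for the short-stay rule: the team did not want to extrapolate from a very short record.

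**Objective 2e (SAP 5.1 and section 2).** The method is that of objective 1, negative binomial regression. "Number of severe events such as pyelonephritis or hospital admission will be the dependent variable". It is evaluated at six and 12 months. No separate missing-data rule is given.

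**Other analysis sets.** The complete case set takes only women with complete data (SAP 5.1.2). For the other set, "A per protocol analysis including patients consuming at least 80% of dispensed study medication will be made".

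**Who leaves (Protocol 4.4.1).** The list of reasons for withdrawal from the study includes an SAE possibly due to the drug and "participating patients developing serious illness making it impossible for them to continue taking the study tablets". The closing paragraph of the same section keeps women who stop the study medication early in normal follow-up, unless they withdraw consent.

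**Other records of these events.** SAP 4.3 registers pyelonephritis, hospitalization and death as safety endpoints. Protocol 4.4.2 compares the arms on serious events related to the study drug or to UTI, as a trigger for stopping the trial.

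**The concern.** The rules were evidently framed with frequent counts in mind. For antibiotic courses, the protocol expects about 1.5 to 2.0 per woman per six months, so a donor mean is a value of ordinary size. For a rare serious event the donor mean is close to zero. Replacing an early leaver's record then removes an event that was actually observed, while scaling a later leaver's record adds part of an event that never occurred.

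The stated reason for the short-stay rule is an argument against scaling up a short record. It is not an argument for discarding what the record contains.

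2e is the only between-arm comparison of these events in the SAP, and the events are also named safety endpoints. If few occur, losing or doubling one or two can visibly shift the estimate.

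**Working it through.** **1. The plan's own figures.** The documents give no event rate, power or sample size for 2e. The only figures to reproduce are those for the primary outcome in Protocol 8.1. The expected counts are that "the intervention group would have an average of 1.5 while the control group is assumed to remain around 2.0". The other inputs are an SD of 1.5 per arm, two-sided alpha 0.05 and 80% power.
- t-test, effect 0.5/1.5: 142.25 per arm, rounded up to 143, total 286. Matches.
- Mann-Whitney, dividing by 3/π: 142.25/0.955 = 148.96, rounded up to 149, total 298. Matches.
- Loss: "after considering a 25% loss to follow-up we aim to include at least 397 patients". 298/0.75 = 397.3. Matches to rounding, and the target of 400 covers it.

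**2. Weight of one observed event in 2e.** With t months completed (t from 3 to under 6), weight = 6/t.

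| Leaves at month | Weight |
|---|---|
| under 3 | 0 (own record replaced by donor mean) |
| 3 | 6/3 = 2.0 |
| 4 | 6/4 = 1.5 |
| 5 | 6/5 = 1.2 |

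Several of these results are not integers, yet SAP section 6 chose the negative binomial model because the outcome is an integer.

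**3. Do the other sets restore the early event?**
- Complete case: no, because leavers are excluded.
- Per protocol: 4 boxes × 90 = 360 tablets are dispensed, and 80% is 288. Under three months at two tablets a day gives about 90 × 2 = 180 at most. She is excluded.

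**4. Size if leaving is unrelated to events.** Assumptions, none from the documents except that 25% is the planned loss: 400 women; event rate r of 0.02–0.10 per six months; a fraction d of 10–25% leaving, uniformly over months 0–6. With L = 400d leavers:
- early observed events (dropped) = L × 0.5 × r × 1.5/6
- late observed events = L × 0.5 × r × 4.5/6, counted as L × 0.5 × r
- events in women who stay = 400(1 − d)r

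At d = 0.25, r = 0.10: early 1.25, late 3.75 counted as 5.00, stayers 30. Share dropped = 1.25/35 = 3.6%. At d = 0.10, r = 0.10: 0.5/38 = 1.3%. The shares do not depend on r.

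**5. Effect on the test under no treatment difference.** Simulation: 2,000 runs per setting, 200 per arm, Poisson events, two-arm log rate ratio without covariates, nominal 5%.

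| Leaving | r | SAP rules | Observed events, time offset |
|---|---|---|---|
| 10% | 0.05 | 5.2% | 4.3% |
| 10% | 0.10 | 5.4% | 4.6% |
| 25% | 0.05 | 6.3% | 3.8% |
| 25% | 0.10 | 7.0% | 4.8% |

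Simulation error is about √(0.05 × 0.95/2000) = 0.5 percentage points. The excess at 25% leaving is beyond that; at 10% it is not.

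**6. Size if events prompt leaving (illustration only).** 200 per arm, k active-arm events in women leaving before month 3, no other leavers, donor mean taken over the rest of the arm. Scored active total = (E − k) + k(E − k)/(200 − k).

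| True events | k | Scored active total | Ratio |
|---|---|---|---|
| 8 vs 4 | 0 | 8 | 2.00 |
| 8 vs 4 | 3 | 5 + 3 × 5/197 = 5.08 | 1.27 |
| 8 vs 4 | 4 | 4 + 4 × 4/196 = 4.08 | 1.02 |
| 6 vs 6 | 2 | 4 + 2 × 4/198 = 4.04 | 0.67 |

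**The case against.** **Reach is inferred.** SAP 5.1.1 does not name 2e, and the authors may have had only the antibiotic and UTI counts in mind. That is possible, but nothing in the text limits the rules. 2e takes over objective 1's approach, and no passage says that observed severe events are retained. An analyst following the SAP would apply the rules.

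**A reader might infer that serious events are erased from the trial, or that no other comparison of them exists.** The documents do not support this. The events remain in the SAE and safety records, and Protocol 4.4.2 compares UTI-related serious events between arms. That comparison is a stopping trigger rather than an effect estimate, so within the SAP 2e stands alone.

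**A reader might infer that the rules fall on exactly the women with events, because illness drives leaving.** This goes too far. Women who only stop the study medication are to stay in follow-up, so those affected are women who withdraw consent, are lost to follow-up or, by the wording, die. No passage says explicitly that death counts as leaving. Protocol 4.4.1 does, however, also list SAE and serious illness as withdrawal from the study, and the two statements do not agree.

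**The 8 versus 4 example is one-sided.** True. At the 3.6% share, about 0.29 of 8 events would be dropped, and three or more of 8 would have a probability of about 0.2%. The example matters only if events cause leaving, for which the documents give no figure.

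**A reader might extend the point to 2c and 2d.** Those outcomes are per-woman medians over episodes and do not accumulate with time. Reading extrapolation as scaling a median is strained, and a median of two episodes can already fall between categories.

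**The same rules overwrite early leavers' antibiotic and UTI counts.** They do, but there the donor mean is not near zero. This point is confined to 2e and the safety endpoints.

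**Conclusion.** The point holds for the 2e intention-to-treat analysis. As written, an observed event in a woman leaving before month 3 is replaced by a near-zero mean, and one in a woman leaving at month 3 to under 6 is weighted 6/t, at most 2.0. The same treatment applies to leavers in the second six months.

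If leaving is unrelated to events, the effect is modest: about 1–4% of observed events dropped and, at 25% leaving with rates of 0.05–0.10, a false-positive rate of about 6–7% against about 4–5% with an offset. If events prompt leaving, the ratio can be materially distorted in either direction. Event rates, the leaving pattern and the simplified test are all assumptions.

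Severity: should-fix, for a secondary and safety objective. The primary conclusion is not affected by the change.

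**What to change.** In SAP 5.1.1, state that for objective 2e and the safety endpoints every observed event is counted once, and that no value is imputed or scaled. In SAP 5.1, add the log of observed time as an offset in the 2e model, for both the six- and 12-month evaluations, with death or leaving ending observation. Report the number of women with at least one event by arm.

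The statements in Protocol 4.4.1 on withdrawal from the study and on continued follow-up should be reconciled, so that SAP 5.1.1 can say who counts as a leaver.

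Cost: a few lines of wording and no new data, since the existing scaling rule already needs the time of leaving. The small downside is that 2e becomes a rate over observed time instead of a six-month count.

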6. REASONS FOR CHANGE FROM ORIGINAL PLANNING

During discussions within the research team we have decided to make some changes to the original statistical analysis plan described in the published study protocol:

- We changed the choice of regression model from standard linear regression to negative binomial regression since the dependent variable is an integer. However, all objectives and choice of independent variables remain unchanged.
- For objective 2c the number of scale steps is only 6 and we decided ordinal regression is a better method than standard linear regression on rank transformed data.
- The statistical analysis of objective 2f was previously described as being done if we had at least 60 observations. In further discussions we decided to clarify this as including as many independent variables as possible if the condition 10 observations for each independent variable is fulfilled. This gives a structure for how to choose independent variables.
- Imputation of data in intention to treat analysis was changed for patients dropping out after participating less than 3 months. We believe it would be a better representation to use the

average from similar patients remaining in the study rather than extrapolating data from a very short time frame.

- In the original study protocol (version 11.1) we first planned an intention to treat analysis as the main analysis, a complete case analysis as a secondary analysis and that a per protocol analysis would not be made. When the study protocol was published we decided to add that a per protocol analysis will also be made (26).

All decisions above were taken before data collection were completed and before any data were analysed.

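### The primary analysis, labelled intention to treat, assumes that women who leave the study keep a same-arm rate after leaving, and no planned analysis tests that assumption

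*SAP*

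**What the plan says.** SAP 5.1.1 labels the primary analysis intention to treat and gives two rules for women who leave during the six treatment months.

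- Leaving before three months: "If they remained for less than three months their observations will be imputed with the mean from similar patients". Similar means the same intervention group and an age within five years. SAP 6 describes the replacement value as the "average from similar patients remaining in the study rather than extrapolating data from a very short time frame".
- Leaving after at least three but before six months: these women "will contribute with data up until they leave the study and this data will be extrapolated as if it was six months".

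Protocol 4.4.1 treats stopping the drug differently from leaving the study. Women who stop IMP early without withdrawing consent "will be followed up in the same framework of the study and in the same way as participants receiving IMP". Their off-drug antibiotic treatments are therefore observed and counted.

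Three other analyses are planned: a sensitivity analysis for incomplete baseline data (SAP 5.1.1), a complete case analysis (SAP 5.1.2), and a per protocol analysis of women who took at least 80% of dispensed medication (SAP 5.1.3).

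**The concern.** Following women after they stop the tablets fits an analysis of allocation, whether or not treatment continues. The rules for leavers fit a different question. In the active arm, both fill the months after departure with a rate formed largely on drug: that of comparable women still in the study, or the woman's own rate before she left. The primary estimate therefore combines observed off-drug outcomes for stoppers who stay with assumed on-drug outcomes for those who go.

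If the effect wanes after stopping, the mixture favours methenamine by an amount that grows with dropout. The reported rate ratio would then be more favourable than the effect in the population as allocated, and nothing in the plan would reveal the difference. Objective 2a treats persistence after discontinuation as an open question, yet these rules assume full persistence for leavers without saying so.

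**Working it through.** **Inputs from Protocol 8.1.**

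- Rate without the drug: the women "will have an average of two courses of antibiotics for suspected UTI every six months".
- Size of effect looked for: "Hence the intervention group would have an average of 1.5 while the control group is assumed to remain around 2.0".
- Spread used in the calculation: "We assume the standard deviation in each group to be 1.5".
- Allowance for loss: "To achieve an effective sample size of at least 298 after considering a 25% loss to follow-up we aim to include at least 397 patients".

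**The plan's own figures reproduce.** The effect size is 0.5/1.5 = 0.33. The exact t-test needs 142.25, so 143 per arm (286 in all). Dividing 142.25 by 3/π gives 148.96, so 149 per arm (298). Then 298/0.75 = 397.3, against a stated 397 and a target of 400.

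**Formula.** Let L be the share leaving in the first six months, f the mean fraction of the six months that leavers have unobserved, and p the share of the drug effect that persists after stopping. Assume that leavers stop the tablets, that dropout is independent of outcome, and that donors are on drug.

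- Placebo mean: 2.0 under either approach.
- Active mean under the SAP rules: 1.5, because both rules return the on-drug rate in expectation.
- Active mean as allocated: 1.5 + L × f × (1 − p) × 0.5.
- Overstatement: L × f × (1 − p) × 0.5 courses, which is L × f × (1 − p) as a share of the assumed effect.

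**Main illustration (L = 0.25, f = 0.5, p = 0).** The overstatement is 0.25 × 0.5 × 0.5 = 0.0625 courses. The effect as allocated is 0.5 − 0.0625 = 0.4375, with rate ratio 1.5625/2.0 = 0.78. The SAP rules give 0.50 and 0.75. The excess is 0.0625/0.5 = 12.5% of the assumed effect, or 0.0625/0.4375 = 14.3% of the effect as allocated. A gamma-Poisson simulation of the SAP rules without age matching gave 0.439 as allocated and 0.501 under the SAP.

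**Split by rule.** With even leaving, 12.5% of women leave before month 3 with 0.75 of the period unobserved on average: 0.125 × 0.75 = 9.4 points. Another 12.5% leave later with 0.25 unobserved: 0.125 × 0.25 = 3.1 points.

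**Range.** The timing of leaving and the value of p are assumptions; the documents give neither.

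| Loss | Timing of leaving | Effect persisting | Overstatement (courses) | Share of 0.5 | Rate ratio as allocated |
|---|---|---|---|---|---|
| 25% | all on day 1 | none | 0.125 | 25% | 0.81 |
| 25% | even, months 0–3 | none | 0.094 | 18.75% | 0.80 |
| 25% | even, months 0–6 | none | 0.0625 | 12.5% | 0.78 |
| 25% | even, months 3–6 | none | 0.031 | 6.25% | 0.77 |
| 25% | all at month 5 | none | 0.021 | 4.2% | 0.76 |
| 25% | even, months 0–6 | half | 0.031 | 6.25% | 0.77 |
| 10% | even, months 0–6 | none | 0.025 | 5% | 0.76 |

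If the arms do not differ, the factor 2.0 − 1.5 becomes 0 and so does the bias.

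**Would another planned analysis show it?** Under independent dropout the complete cases have means 2.0 and 1.5, a difference of 0.50; simulation runs gave 0.49 to 0.50. This agrees with the SAP result and not with 0.4375. The per protocol set selects women who took most of their tablets, so it moves further from the off-drug months.

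**The case against.** Several points on the other side stand.

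- **Size and consequence.** At 200 per arm the standard error of the difference is 1.5 × √(2/200) = 0.15, so 0.0625 is about 0.4 of a standard error. Power at a difference of 0.4375 is still 83% with 200 per arm (71% with 149). A reader might infer that the rules could manufacture a benefit. Under independent dropout they inflate a real effect and add no bias where there is none. The understated variance from single imputation is a separate matter.
- **The 12.5% is conditional.** Protocol 8.1 gives no period for the 25%, and follow-up runs to day 360, so loss in the first six months may be smaller. Neither even leaving nor immediate loss of effect is stated anywhere.
- **The credit is partial.** A reader might infer that every active-arm leaver is credited with six months of drug effect after stopping. Only leavers before month 3 receive other women's mean; later leavers keep their own rate. The donors need only be in the study, so their mean can include off-drug time.
- **Leaving need not mean being off drug.** Tablets for the full six months are handed out (Protocol 5.1), so a woman lost to follow-up may still take them. The GP record check at the end of the project (Protocol 3.4) may also recover some treatments.
- **Informative dropout is a different mechanism.** If each treatment triggers leaving with 16% probability, the rate ratio is 0.785 as allocated and 0.729 under the SAP rules. With full persistence, and so no off-drug credit, it is still 0.751 against 0.730. Thus 0.021 of the 0.056 gap, over a third, is not due to this point.
- **The assumption predates the SAP.** Protocol 8.2 already rescaled partial data, with the same expected bias under these assumptions.

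These points limit the size. They leave the mismatch between the two sets of women, and the absence of any analysis that tests the assumption.

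**Conclusion.** The point holds in a conditional form. The text of SAP 5.1.1 and Protocol 4.4.1 alone shows that the primary analysis treats off-drug time in two ways, depending on whether a woman stays in follow-up. If leavers stop the tablets and the effect fades, a real effect is overstated by the share leaving in the first six months times the mean fraction unobserved. At 25% loss this runs from about 0 to 25% of the assumed effect, with 12.5% under even leaving and immediate loss of effect. It shrinks with later leaving, lower loss, persistence, continued tablet use or off-drug donors.

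A reader might go further and conclude that placebo-rate imputation must become the primary analysis, or that any claim of benefit should depend on its agreement. The documents do not support that. Persistence is itself under study in objective 2a, and no IMP stop date is among the variables listed in Protocol 6 or SAP 4. The supported conclusion is that the assumption should be stated and tested beside the primary result.

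**What to change.** Three changes to SAP 5.1.1:

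1. Keep every leaver's observed treatments and observed follow-up time. Handle only the unobserved months, through a log follow-up-time offset in the negative binomial model or through multiple imputation, in place of mean imputation and extrapolation.
2. State that this primary analysis assumes the same-arm rate continues after leaving. An offset or same-arm multiple imputation avoids treating filled-in values as observed, but does not remove the bias described here.
3. Pre-specify one control-based multiple-imputation sensitivity analysis. Draw active-arm leavers' unobserved months from the placebo-arm rate given the baseline covariates, and report the result beside the primary one.

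The cost is a paragraph of SAP text and one standard multiple-imputation run. It needs each leaver's date of leaving, which the existing extrapolation rule already requires, but no IMP stop date. The downside is that the sensitivity estimate will be slightly less favourable, and conservative if the effect outlasts treatment or leavers keep taking the tablets. The SAP should say so where it defines the analysis.
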